#### **5.4.3** Multiple Evaluations

After all the records have been slotted based on study day, if there are multiple valid records for an assessment within an assigned analysis visit, only one of these records will be used for summary statistics and analyses. The record to be used is determined using the following hierarchy (in decreasing order):

- the record closest to the target visit day
- the record with an original nominal visit that matches the analysis visit

\*\* Week 97 is the 1 week post-treatment follow-up visit for those subjects completing the study per protocol. The 1 Week Follow-up Visit is the 1 week post-treatment follow-up visit for those subjects who withdraw early from active treatment.

• the record earliest in time

For missing values prior to Week 24 where the LOCF algorithm is applied, it is always the last valid assessment on treatment carried forward even though this might not be the assessment obtained by the above hierarchy and used in the summaries by visit.

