6.9 Adverse Events Assessments

6.9.1 Definitions

An adverse event (AE) is defined as any new medical problem, or exacerbation of an existing problem, experienced by a subject while enrolled in the study, whether or not it is considered drug-related by the investigator.

A serious adverse event (SAE) includes any event that results in any of the following outcomes:

- death
- life-threatening, i.e., the subject was, in the opinion of the investigator, at immediate risk of death from the event as it occurred. It does not include an event that, had it occurred in a more severe form, might have caused death.
- persistent or significant disability/incapacity
- requires in-patient hospitalization or prolongs hospitalization
- congenital anomaly/birth defect
- other medically significant events that, based upon appropriate medical judgment, may jeopardize the subject and may require medical or surgical intervention to prevent one of the outcomes listed above, e.g., allergic bronchospasm requiring intensive treatment in an emergency room or home, blood dyscrasias or convulsions that do not result in hospitalization, or the development of drug dependency or drug abuse.

Non-serious adverse events are all events that do not meet the criteria for a "serious" adverse event.

Immediately Reportable Adverse Event (IRAE): Any serious adverse event or any adverse event that necessitates discontinuation of study drug, including pregnancy.

Clinical Laboratory Changes: It is the investigator's responsibility to review the results of all laboratory tests as they become available. For each abnormal laboratory test result, the investigator needs to ascertain if this is an abnormal (i.e., clinically significant) change from baseline for that individual subject. (This determination, however, does not necessarily need to be made the first time an abnormal value is observed. The investigator may repeat the laboratory test or request additional tests to verify the results of the original laboratory tests). If this laboratory value is determined to be an abnormal change from baseline for that subject, this is considered an AE.

High serum or plasma glucose (hyperglycemia) and high HbA1c, the disease related morbidity, are being followed as the study endpoints and will not be documented as adverse events. If, however, the event fulfills any of the criteria for a "serious" adverse event, it must be recorded and reported as such.

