### 5.4.2 Visit Slotting Algorithm

For all safety and efficacy parameters to be summarized or analyzed by visit, data records will be slotted to one of the protocol specified visits using the following algorithm:

- a) Determine the study day for all records using the algorithms from Section 5.4.1
- b) For all records (including unscheduled visit records, early withdrawal records and repeat visit records), use the study day determined above with the slotting intervals in the analysis visit window table below to slot the record to the appropriate analysis visit.

Final – 22November2011 CONFIDENTIAL Page 17 of 30

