**Table 2: Analysis Visit Windows** 

Scheduled Visit	Target Study Day of Visit	Slotting Intervals
Week -5 (Screening)	-35	<=-25
Week -2	-14	-24 to -4 days
Baseline (Week 0)	1	-3 to 1 days
Week 2	15	2 to 29 days
Week 6	43	30 to 64 days
Week 12	85	65 to 106 days
Week 18	127	107 to 148 days
Week 24	169	149 to 211 days
Week 36	253	212 to 295 days
Week 48	337	296 to 379 days
Week 60	421	380 to 463 days
Week 72	505	464 to 547 days
Week 84	589	548 to 631 days
Week 96 (End of Treatment	673	632 to (last dose date)
Visit)*		
Week 97**	680	>Last dose date + 7 days
1 Week Follow-up Visit**	Last dose date + 7 days	>Last dose date + 7 days

\* Week 96 is the end of treatment visit for those subjects completing the study per protocol. For subjects who withdraw early from active treatment, the end of treatment visit will be assigned to an analysis visit based on the visit slotting algorithm using study day.

For parameters which were not scheduled to be collected at all visits, still use the all-inclusive visit intervals defined for all visits (that is, the visit window table above) to slot records. However, if a value is slotted to a visit unscheduled for a parameter, it will not be summarized except for summaries focusing on extreme values such as laboratory shift tables. These records will also be included in data listings.

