#### **9.2** Labs

### 9.2.1 Hematology, Chemistry and Urinalysis

Laboratory parameters include the following tests: hematology, chemistry, and urinalysis. Established or generally acknowledged methods, normal ranges, and quality control procedures will be supplied by the local and central laboratory for the study records.

Hematology parameters used in summaries include hematocrit, hemoglobin, platelet count, red blood cell (RBC) count, and white blood cell (WBC) count with differential. Chemistry

Final – 22November2011 CONFIDENTIAL Page 27 of 30

parameters (including lipids) used in summaries include albumin, ALT, AST, blood urea nitrogen, calcium, bicarbonate, chloride, direct bilirubin, glucose, magnesium, phosphorus, potassium, sodium, total bilirubin, total protein, uric acid, total cholesterol, LDL cholesterol, HDL cholesterol, triglycerides, and ApoB. Urinalysis parameters used in summaries include appearance, bilirubin, color, glucose, ketones, microscopic examination of sediment, nitrites, occult blood, pH, protein, specific gravity, and urobilinogen.

All laboratory parameters will be summarized for each treatment group, at every assessed time point using descriptive statistics and graphical displays of the means and standard deviations over time. In addition, for hematology and chemistry laboratory parameters, changes from baseline in these quantitative tests will be summarized by treatment group and at every assessed post-baseline time point.

Shift tables will be developed by first classifying the subject laboratory results as low, normal, or high in comparison to the applicable laboratory reference range. The number and percentage of subjects with indicated shifts (low, normal, high) in their results from baseline to each post-baseline assessment will be presented for all hematology, chemistry and applicable urinalysis parameters. All laboratory data will be listed.

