#### **9.4 ECGs**

Each ECG parameter at each assessed time point will be summarized by treatment group using descriptive statistics and presented graphically. Change from baseline will also be summarized. A summary of the number and percentage of subjects on overall ECG interpretation and abnormal findings will be displayed by treatment group.

Additionally, a summary of the number and percent of subjects who experience QT  $\geq$ 450 msec, QT  $\geq$ 480 msec, QT  $\geq$ 500 msec, QTcB  $\geq$ 450 msec, QTcB  $\geq$ 480 msec, QTcB  $\geq$ 500 msec, QTcF  $\geq$ 480 msec, QTcF  $\geq$ 500 msec will be provided,

All ECG data will be listed.

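### When an unscheduled or repeat lab or ECG shares a visit slot with a scheduled record, timing rather than severity decides which enters the shift and QT tables

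*SAP*

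**What the plan says.** SAP 5.4.2 sets the scope of visit slotting: "For all safety and efficacy parameters to be summarized or analyzed by visit". The records that enter it are all records, "including unscheduled visit records, early withdrawal records and repeat visit records". SAP 5.4.3 then deals with slots holding more than one valid record for an assessment: "only one of these records will be used for summary statistics and analyses". The order of preference is nearness to the target day, then a matching nominal visit, then the earlier record. How abnormal the value is plays no part, and safety tables are not exempted.

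One exception stands in the text under SAP Table 2: "if a value is slotted to a visit unscheduled for a parameter, it will not be summarized except for summaries focusing on extreme values". Laboratory shift tables are its only named example.

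SAP 9.2.1 describes the shift tables as "The number and percentage of subjects with indicated shifts (low, normal, high) in their results from baseline to each post-baseline assessment". SAP 9.4 promises "a summary of the number and percent of subjects who experience QT" and QTc at or above stated thresholds. Shells 14.3-2.4 to 14.3-2.6 and 14.3-4.3 are laid out by visit and ask for every available timepoint. None has a row for the worst post-baseline value.

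The protocol expects extra records. Section 6.5 allows ECGs when clinically indicated, and section 6.9.1 says "The investigator may repeat the laboratory test or request additional tests to verify the results of the original laboratory tests".

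**The concern.** Closest-to-target selection is a sensible rule for by-visit means. It suits shift and threshold tables poorly, because their purpose is to show how many subjects in each arm had an out-of-range value. Tests done for cause are mostly done between visits, so they tend to lie further from the target day than the scheduled record and lose to it.

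The exception under Table 2 shows that the authors wanted shift tables to catch extremes. It turns on whether the visit was scheduled for the parameter, so it does not reach a second record in a slot that already holds a scheduled one; there SAP 5.4.3 governs. For a lab drawn at every visit the exception never applies. At stake are the by-arm counts of abnormal laboratory and QT values, which could omit peaks seen between visits.

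**Working it through.** The plan states no figure on this point, so the check counts days in its own windows.

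**Inputs**
- Slots and target days: SAP Table 2.
- Visit tolerance: SAP Table 1, note 1 (±3 days to Visit 8, ±6 days after). The protocol (section 7 and Appendix 1) gives ±7 days, with ±3 at Week 2.
- What is drawn when: SAP Table 1, ECG row and note 4.
- Assumptions: a scheduled record is present in the slot, and the extra test is equally likely on any other day of the slot. The documents give no rate or timing of unscheduled testing.

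**Formula.** Let a slot have L days and the scheduled record lie k days from target. The extra record is chosen only if strictly nearer, because a tie goes to the record whose nominal visit matches. From Week 2 to Week 84 every slot extends at least 13 days either side of target, so 2k − 1 of the L − 1 other days are nearer:
- scheduled record k ≥ 1 days off target: share = (2k − 1)/(L − 1), and zero when k = 0;
- scheduled record uniform over ±m days: share = 2m²/[(2m + 1)(L − 1)].

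**Share of the time the extra record is selected**

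| Slot | L | SAP, uniform | SAP, window edge | ±7, uniform | ±7, window edge |
|---|---|---|---|---|---|
| Week 2 | 28 | 18/189 = 9.5% | 5/27 = 18.5% | 98/405 = 24.2% | 13/27 = 48.1% |
| Week 6 | 35 | 18/238 = 7.6% | 5/34 = 14.7% | 98/510 = 19.2% | 13/34 = 38.2% |
| Weeks 12, 18 | 42 each | 18/287 = 6.3% | 5/41 = 12.2% | 98/615 = 15.9% | 13/41 = 31.7% |
| Week 24 | 63 | 18/434 = 4.1% | 5/62 = 8.1% | 98/930 = 10.5% | 13/62 = 21.0% |
| Weeks 36–84 | 84 each | 72/1079 = 6.7% | 11/83 = 13.3% | 98/1245 = 7.9% | 13/83 = 15.7% |
| Weighted by L, Days 2–631 (630 days) | | 6.5% | 12.9% | 10.6% | 21.0% |

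The extra record is therefore not selected 93.5% to 87.1% of the time under the SAP windows, and 89.4% to 79.0% at ±7 days. Using the protocol's ±3 at Week 2 changes the last two selection shares little: 10.6 − 28 × (24.2 − 9.5)/630 = 9.9%, and 21.0 − 28 × (48.1 − 18.5)/630 = 19.7%. Week 96 is left out of this table because its slot ends at the last dose.

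**Where a scheduled record competes.** Adding a 42-day Week 96 slot (last dose assumed on Day 673) gives 630 + 42 = 672 days. The last column runs from a scheduled visit 7 days off target to one exactly on target.

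| Parameter | Days in slots with a scheduled record | Days on which the extra record loses |
|---|---|---|
| CBC, electrolytes, BUN, creatinine | 672 (100%) | 524–661 (78.0–98.4%) |
| ALT, AST, bilirubin | 672 − (28 + 35 + 42) = 567 (84.4%) | 461–559 (68.6–83.2%) |
| ECG | 63 + 84 + 42 = 189 (28.1%) | 153–186 (22.8–27.7%) |

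Liver tests are not scheduled at Weeks 2, 6 and 18, so values in those 105 days (15.6%) are kept in the shift tables by the exception. ECGs are scheduled on treatment only at Weeks 24, 60 and 96. On the other 483 days (71.9%) a lone extra ECG has no competitor, but whether the QT table counts as an extreme-value summary is not stated.

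**A retest can displace the abnormal value.** With target Day 85, a scheduled abnormal value on Day 82 is 3 days off and a normal retest on Day 87 is 2 days off, so the retest is used. This needs the scheduled visit to precede the target. If it falls on or after the target, any later retest in the slot is further away and the scheduled value stays.

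**The case against.** A reader might infer that for-cause lab and ECG values in general are dropped, and that a drug-related excess could vanish from every by-arm table. The documents do not support that, for four reasons.

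- **The exception does real work.** It keeps liver tests at Weeks 2, 6 and 18 in the shift tables, and for ECG most of the treatment period has no competing record. The call in the shells for all available timepoints fits keeping such records. The 87–94% range cannot be applied to labs and ECGs together.
- **Adverse-event tables are a separate route.** Under protocol 6.9.1, liver tests above 3 times the upper limit, a creatinine rise of 0.5 mg/dL or more, and any change the investigator judges abnormal for that subject are adverse events. SAP 9.1.1 tabulates treatment-emergent events by arm, with no visit slotting. All lab and ECG data are listed, and clinically significant abnormal labs have their own listings (14.3-12.1 to 14.3-12.3).
- **87% is not a floor.** It requires every scheduled visit to be present and inside the SAP window. A missed or late visit lets the extra record in.
- **A dropped record is not always the worst one.**

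All four stand, and they limit the size of the point. They do not close the gap. Outside the liver and creatinine rules, the adverse-event route depends on investigator judgement, and listings give no rates by arm. The all-timepoints instruction adds visits, not further records within a visit.

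**Conclusion.** The point holds in a limited form. SAP 5.4.3 selects safety records by timing, and the exception in 5.4.2 does not cover a second record in a slot that already has a scheduled one. Abnormal values can therefore be absent from the by-visit shift and QT tables, and no worst-post-baseline row recovers them.

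The effect is largest for labs drawn at every visit: the extra record is unused about 87–94% of the time under the SAP windows and about 79–89% at ±7 days. These are shares of days under the stated assumptions, not shares of observed events. Creatinine is drawn at every visit, but the chemistry list in SAP 9.2.1 does not name it, so its place in the shift tables should be confirmed. The effect is smaller for ALT, AST and bilirubin. For ECG, competition is confined to 28% of days; on the rest, the treatment of a lone extra ECG is undefined. The wording of 9.4, which counts subjects with no visit limit, and a shell laid out by visit also leave the QT count open to two readings.

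The primary efficacy result is not affected. This is a worthwhile improvement to safety reporting that brings the tables into line with the SAP's own intent for extreme values.

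**What to change.** 1. Extend the exception in SAP 5.4.2, with a cross-reference in 5.4.3, so that extreme-value summaries use every post-baseline record, scheduled or unscheduled, including several records within one slot.
2. State that the exception covers the QT threshold table (14.3-4.3) as well as the laboratory shift tables.
3. Add a baseline-to-worst-post-baseline shift, in the low and high directions, to Tables 14.3-2.4 to 14.3-2.6.
4. Add an any-post-baseline block to Table 14.3-4.3 giving the maximum QT, QTcB and QTcF per subject, which also settles the reading of 9.4.
5. Keep closest-to-target selection for the by-visit summaries.

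The cost is SAP wording and a little programming. No new data are needed.

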### 5.5 Site Pooling

The study will be conducted at approximately 35 US and international study sites and 4 countries (United States, Mexico, Columbia, and India). Sites will be pooled if appropriate for exploratory efficacy analyses detailed in Section 7.3. Within each country, all sites will be pooled together to form one pooled site, so that a total of 4 pooled sites are available for analyses. At the end of the study, if any single country (such us United States) enrolls significantly more subjects than any other country, a further break-down within that country might be considered as part of the pooling strategy (i.e., regions within United States may be utilized as pooled sites).

## 6 Demographics, Baseline Characteristics, and Medications

### **6.1 Subject Disposition and Withdrawals**

The number of subjects who were randomized and the number of subjects within each analysis set (Safety, Full, Per Protocol) will be summarized for each treatment group. A summary of subjects randomized by country and site will also be provided by treatment group.

Subject status in study participation will be summarized in relation to completion of active treatment through Week 24, and in relation to completion of study. Reasons for early discontinuation of study will be summarized for each treatment group.

Subject disposition data will be listed as well. All disposition summaries will be performed using all randomized subjects. A by-country summary will be provided as well.

The number of subjects who were run-in failures, and the number of subjects who failed to fulfill one or more of the inclusion/exclusion criteria will be tabulated and listed for all run-in failure subjects.

## 6.2 Demographics and Subject Characteristics at Baseline

Demographic data (age, gender, race, ethnicity), baseline characteristics (height, weight, BMI, child bearing potential, baseline HbA1c category) will be summarized.

Final – 22November 2011 CONFIDENTIAL Page 19 of 30

Subject age (years) will be calculated as the full years passed since birth date until the date of informed consent signed:

Age=integer part of [(date of informed consent signed – date of birth + 1) / 365.25].

The BMI will be calculated in kg/m^2:

 $BMI = body weight [kg] / (height [m])^2$ 

Demographic data and baseline characteristics will be tabulated for each analysis set. Baseline comparability of treatments for demographic and baseline characteristics will be assessed using ANOVA model statistics for continuous variables and chi-square statistics for categorical variables. A by-country summary will be provided using the safety analysis set.

Summary of substance (alcohol, tobacco, and drug) use (both categorical and quantitative) will be produced as well as a by-subject listing. All summaries will be performed using the safety analysis set.

### 6.3 Medical History

The number and percentage of subjects with medical history condition will be reported by treatment group. A summary of duration of diabetes disease history in years will be provided. The duration of diabetes disease history is calculated as the years lapsed between screening visit date and type 2 diabetes diagnosis date. For partial missing diagnosis date, the missing month is imputed as January and the missing day is imputed as the first of the month to calculate duration. All other detailed diabetes medical history will be summarized in total, and by country.

In addition, a by-subject listing for detailed diabetes medical history will be provided, and all other medical history data will be listed. All summaries will be performed using the safety analysis set.

## 6.4 Prior/Concomitant Medications

Any prior and concomitant medication used during the study will be recorded and coded using World Health Organization Drug Dictionary (WHODRUG) enhanced version June 2011 to obtain a preferred term (PT) and an anatomical/therapeutic/chemical (ATC) level 4 term. Summary of all medications by treatment group, ATC level 4 term and preferred term will be provided.

The date and time of first dose of study drug will be used as cutoff time point for definition of prior and concomitant medication. Prior medications are those started before the first dose of double-blind study drug. Concomitant medications are those taken at any time on or after the

Final – 22November2011 CONFIDENTIAL Page 20 of 30

day of the first dose of double-blind study drug, including those medications that were started prior to randomization but were continued into the double-blind treatment period.

Partial start dates of prior and concomitant medications will be assumed to be the earliest possible date consistent with the partial date. In the case of a missing year, the year will be assumed to be the year part of informed consent date of that subject. In the case of a completely missing start date, the start date will be assumed to be prior to date of the first administration of study drug. Partial stop dates of prior and concomitant medications will be assumed to be the latest possible date consistent with the partial date. In the case of completely missing stop date, medication will be assumed to be ongoing.

All recorded anti-diabetic medications will be included in the medication summaries described above. Those anti-diabetic medications that the investigators indicated as being rescue medications for hyperglycemia will also be summarized separately by treatment group. The number and percent of subject who are rescued for hyperglycemia over time will be tabulated.

All prior and concomitant medications will be listed. All summaries will be performed using the safety analysis set.

## 7 Efficacy

## 7.1 Primary Efficacy Analyses

The primary efficacy endpoint is HbA1c change from baseline at Week 24. The primary hypothesis is that EGT0001442 reduces HbA1c after 24 weeks of treatment when compared to placebo controls. The Week 24 mean change from baseline will be analyzed using a 2 sample t-test between treatment groups. The primary analyses will be performed on the full analysis set using the LOCF algorithm. Subjects who are rescued for hyperglycemia before Week 24 will have their HbA1c recorded at the time of rescue and carried forward for primary analyses. Subjects who discontinue from active treatment due to any reason before Week 24 will also have their last post-baseline HbA1c observation carried forward for the analyses.

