9.5.1 Primary Efficacy Endpoint

The primary hypothesis is that EGT0001442 reduces HbA1c after 24 weeks of treatment when compared to placebo controls. Change in HbA1c will be estimated as HbA1c at 24 weeks minus HbA1c at baseline. The two groups will be compared with a t-test at a significance level of 0.05. For subjects that receive rescue medication due to hyperglycemia, the last HbA1c prior to receiving rescue medication will be carried forward to week 24.

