### 3.6.1 Week 24 Analysis

A limited unblinded analysis will be performed after all subjects have achieved the Week 24 primary efficacy endpoint (at the Week 24 visit), after all subject data up to Week 24 have been cleaned and locked. The purpose of the analysis will be to support management decisions about continuing the EGT0001142 development program. The unblinded results will be provided to a limited number of recipients at Theracos, and will not be made available to any other personnel involved in the study conduct. Subjects will continue to receive their randomized treatment in a blinded manner for the remainder of the planned 96 weeks of treatment and the follow-up phase.

Final – 22November2011 CONFIDENTIAL Page 13 of 30

The Week 24 analysis will be treated as an interim analysis with regard to the blinding and data handling. Since the primary efficacy analysis is conducted once at the Week 24 time point, no multiplicity adjustment will be used for the interim analysis.

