#### 7.3.2 Analysis of Covariance

To assess treatment effect adjusted for important covariates on HbA1c change from baseline, an analysis of covariance (ANCOVA) model will be performed in supportive of the primary and secondary efficacy analyses. HbA1c change from baseline by visit will be analyzed using an ANCOVA model with treatment group, site (pooled as necessary), gender (male versus female), race (categorized as white, black, and other non-white), and age (categorized as <65 years, and ≥65 years) as factors and baseline HbA1c as a continuous covariate. One analysis will be performed using the LOCF algorithm for all visits, and a separate analysis will be performed using OC algorithm. The OC algorithm analysis will exclude any post-rescue values.

As with HbA1c, ANCOVA analyses will also be performed on change from baseline of body weight, systolic blood pressure, diastolic blood pressure, and FPG. For each of these endpoint, the ANCOVA model will include treatment group, site (pooled as necessary), gender (male versus female), race (categorized as white, black, and other non-white), age (categorized as <65 years, and ≥65 years), and baseline HbA1c category (≥7 to <8.5% versus ≥8.5 to ≤10%) as factors and corresponding baseline endpoint measures (i.e., baseline FPG for FPG change from baseline ANCOVA mode) as a continuous covariate. All analyses will be performed on the full analysis set.

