## Table 14.2-1.1 Analysis of Change from Baseline in HbA1c (%) at Week 24 (Full Analysis Set - LOCF)

Week 24

	EGT0001442	Placebo
	(N=xxx)	(N=xxx)
Number of Subjects [1]	xxx	xxx
Number (%) of Values Carried Forward	xx (xx.x%)	xx (xx.x%)
Baseline		
Mean (SD)	xx.xx (xx.xxx)	xx.xx (xx.xxx)
Median	xx.xx	xx.xx
Min, Max	xx.x, xx.x	xx.x, xx.x
Week 24		
Mean (SD)	xx.xx (xx.xxx)	xx.xx (xx.xxx)
Median	xx.xx	xx.xx
Min, Max	xx.x, xx.x	xx.x, xx.x
Change from Baseline		
Mean (SD)	xx.xx (xx.xxx)	xx.xx (xx.xxx)
Median	xx.xx	xx.xx
Min, Max	xx.x, xx.x	xx.x, xx.x
p-value [2]	0.xxxx	
Model-Adjusted Change from Baseline [3]		
LS Mean (SE)	xx.xx (xx.xxx)	xx.xx (xx.xxx)
95% Confidence Interval	(xx.xx, xx.xx)	(xx.xx, xx.xx)
Difference from Placebo [3]		
Difference of LS Means	xx.xx	
95% Confidence Interval	(xx.xx, xx.xx)	
p-value	0.xxxx	

Note: This analysis uses the last observation carried forward (LOCF) method for missing post-baseline values as well as for values obtained after hyperglycemia rescue. \* indicates statistical significance at 0.05 level.

- [1] Number of subjects with a value at baseline and at the specified visit.
- [2] The p-value is from a two-sided t-test for the difference in means of change from baseline.
- [3] Based on ANCOVA: Change = trt + baseline HbAlc + site + age category + gender + race.

Source Data: Listing 16.2-7.1

Table 14.2-1.2

Analysis of Change from Baseline in HbA1c (%)
(Full Analysis Set - LOCF)

Week 2

	EGT0001442	Placebo	
	(N=xxx)	(N=xxx)	
Number of Subjects [1]	xxx	xxx	
Number (%) of Values Carried Forward	xx (xx.x%)	xx (xx.x%)	
Baseline			
Mean (SD)	xx.xx (xx.xxx)	xx.xx (xx.xxx)	
Median	xx.xx	xx.xx	
Min, Max	xx.x, xx.x	xx.x, xx.x	
Week 2			
Mean (SD)	xx.xx (xx.xxx)	xx.xx (xx.xxx)	
Median	xx.xx	xx.xx	
Min, Max	xx.x, xx.x	xx.x, xx.x	
Change from Baseline			
Mean (SD)	xx.xx (xx.xxx)	xx.xx (xx.xxx)	
Median	xx.xx	xx.xx	
Min, Max	xx.x, xx.x	xx.x, xx.x	
p-value [2]	0.xxxx		
Model-Adjusted Change from Baseline [3]			
LS Mean (SE)	xx.xx (xx.xxx)	xx.xx (xx.xxx)	
95% Confidence Interval	(xx.xx, xx.xx)	(xx.xx, xx.xx)	
Difference from Placebo [3]			
Difference of LS Means	xx.xx		
95% Confidence Interval	(xx.xx, xx.xx)		
p-value	0.xxxx		

Note: This analysis uses the last observation carried forward (LOCF) method for missing post-baseline values as well as for values obtained after hyperglycemia rescue. \* indicates statistical significance at 0.05 level.

- [1] Number of subjects with a value at baseline and at the specified visit.

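### The primary Week 24 HbA1c test is an unadjusted t-test that forgoes baseline HbA1c and has no matching difference or confidence interval in its own table; both come from an ANCOVA the SAP calls supportive

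*SAP*

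**What the plan says.** SAP 7.1 defines the primary analysis on the full analysis set with LOCF: "The Week 24 mean change from baseline will be analyzed using a 2 sample t-test between treatment groups". Protocol 9.5.1 names the same test: "The two groups will be compared with a t-test at a significance level of 0.05". Neither section names a treatment-difference estimate or confidence interval to go with it.

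The ANCOVA sits in SAP 7.3.2, under the exploratory analyses, with its role stated: "an analysis of covariance (ANCOVA) model will be performed in supportive of the primary and secondary efficacy analyses". Its covariates are baseline HbA1c, pooled site, gender, race and age category.

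The primary table shell, Table 14.2-1.1, shows both analyses. Under the arm-level change it prints one p-value, with the footnote "The p-value is from a two-sided t-test for the difference in means of change from baseline". Below that are adjusted arm means, then a difference from placebo with a 95% CI and its own p-value. The footnote to those rows begins "Based on ANCOVA: Change = trt + baseline" and goes on to list HbA1c, site, age category, gender and race. No row is labelled primary or supportive.

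**The concern.** A primary result should be one coherent set: a test, the estimate it tests, and the interval that corresponds to it. Here the test comes from one model and the displayed effect from another. If the two fall on different sides of 0.05, the table shows a conclusion from the t-test beside an interval that does not correspond to it.

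The second issue is efficiency. Baseline HbA1c is collected at Visit 3 for every randomized subject. Adjusting for it costs one degree of freedom and reduces residual variance in proportion to the square of its correlation with change. The plan uses this covariate in the supportive model but not in the primary one.

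**Working it through.** **Inputs from the documents (SAP 3.5, 7.1):** difference 0.4, SD of change 1.0 in both arms, two-sided alpha 0.05, 133 evaluable per arm, 150 enrolled per arm. Neither document gives a baseline SD, a baseline-change correlation r or an ANCOVA residual SD, so r is assumed.

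**1. The plan's own figure.** Noncentrality = 0.4 / (1.0 × √(2/133)) = 3.262, with 264 df and critical value 1.969. Power is 90.1%. With 132 per arm it is 89.9%, so 133 is the smallest n reaching 90% and the SAP's figure reproduces. The protocol's 131 gives 89.7%, which is also approximately 90%. With 150 per arm, power is 93.2%.

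**2. Adjusting for baseline.** Residual SD = 1.0 × √(1 − r²), with 263 df at 133 per arm. CI half-width = 1.969 × residual SD × √(2/n). No credit is given here for stratified randomization.

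| abs(r) | Residual SD | Power, 133/arm | Gain, 133/arm | Half-width, 133/arm | Gain, 150/arm |
|---|---|---|---|---|---|
| 0 (t-test) | 1.000 | 90.1% | – | 0.241 | – |
| 0.05 | 0.999 | 90.2% | 0.1 | 0.241 | 0.1 |
| 0.2 | 0.980 | 91.3% | 1.1 | 0.237 | 0.9 |
| 0.3 | 0.954 | 92.6% | 2.5 | 0.230 | 1.9 |
| 0.4 | 0.917 | 94.4% | 4.2 | 0.221 | 3.2 |
| 0.5 | 0.866 | 96.3% | 6.2 | 0.209 | 4.6 |

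**3. Credit for stratification.** Randomization is stratified on screening HbA1c at 8.5% (SAP 3.4). This already balances part of the baseline and raises the t-test's own power. In a simulation (8,000 runs per cell, assumed baseline SD 0.70) the gain at 133 per arm was 0.6, 1.5, 2.6 and 3.8 points at r = 0.2, 0.3, 0.4 and 0.5. At 150 per arm it was 0.3, 1.1, 2.1 and 2.6.

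**4. What r might be.** With baseline SD s_b, baseline-to-Week-24 correlation c and SD of change 1, the Week 24 SD s_w solves s_b² + s_w² − 2·c·s_b·s_w = 1, and r = c·s_w − s_b. Assume s_b = 0.8. For c = 0.5, 0.6 and 0.7, r is −0.24, −0.05 and +0.17; for c = 0.4 and 0.8 it is −0.40 and +0.41. With s_b = 0.87 and c = 0.5, 0.6 and 0.7, r is −0.32, −0.13 and +0.11. Plausible inputs therefore run from no correlation to about 0.4 in size, and the gain cannot be fixed at one figure.

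**5. How often the two analyses disagree.** Simulation of 266 patients in 35 centers, with the SAP's ANCOVA on 4 pooled countries and a difference of 0.4. Assumptions: centers split 17/6/6/6 by country, blocks of 4 within center and HbA1c stratum, screening-baseline correlation 0.9; 8,000 runs. At r = 0.05, 0.2 and 0.3:
- With no effect of the other covariates, the two disagree at 0.05 in 2.0%, 2.7% and 3.7% of trials.
- If country, sex and age explain 5% of variance (assumption), the figures are 2.8%, 3.5% and 4.3%.
- Across these scenarios, the t-test is significant with an ANCOVA CI that includes zero in 0.9–1.4%; the opposite occurs in 0.6–3.4%.
- The unadjusted and ANCOVA differences are on average 0.014–0.029 HbA1c points apart.

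A simpler simulation at r = 0.4–0.5 gave 4.5–5.0% disagreement.

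**6. Validity.** With no treatment effect, simulated type I error at r = 0.05, 0.2 and 0.3 was 0.053, 0.052 and 0.048 for the t-test and 0.054, 0.053 and 0.051 for the baseline-only ANCOVA. Neither shows a problem.

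**The case against.** The best defence is that nothing is ambiguous or lost. This is largely right, and it limits the point in five ways.

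- **Which analysis is primary.** A reader of the table alone might infer that the plan never says. The documents do not support that: SAP 7.1 and protocol 9.5.1 name the t-test, SAP 7.3.2 calls the ANCOVA supportive, and the footnotes identify each source. What stands is that the table carries no such label.
- **Missing information.** A reader might infer that the unadjusted effect cannot be recovered. It can: the shell prints n, mean and SD of change per arm, so the difference and its CI follow by arithmetic. The ANCOVA block is also coherent, with its own p-value beside its own CI.
- **Validity and power.** A reader might infer that omitting baseline undermines the trial. It does not. The t-test is valid and reaches its planned power unaided, and if r is near zero adjustment gains nothing. Changing the primary model is an improvement, not the repair of an error.
- **Site pooling.** SAP 5.5 leaves the ANCOVA's site term open at the end of the study ("a further break-down within that country might be considered as part of the pooling strategy"), while SAP 3.6.1 says "A limited unblinded analysis will be performed after all subjects have achieved the Week 24 primary efficacy endpoint". A reader might infer that the displayed estimate could be steered. But the pooling applies to the exploratory analyses, the trigger is enrolment by country, and the unblinded Week 24 results go to a limited group. In simulation, splitting the largest country into four regions changed ANCOVA significance in only 0.6–0.8% of trials. This is minor.
- **Confidence intervals for secondary results.** SAP 5.2 promises them without naming a model, and the FPG, weight and blood pressure tables do show CIs. No breach follows.

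Also, the protocol available is the one dated 02 February 2011. The SAP refers to versions of April, August and September 2011, so the test named in the current protocol should be confirmed.

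**Conclusion.** The point holds as a modest one. Two facts rest on the documents alone: the primary test omits a covariate that the plan already collects and already models, and the primary table gives that test no estimate or CI of its own, taking both from the supportive model without labelling them.

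The sizes rest on assumptions. The power gain is negligible if r is near zero and reaches 2 points at |r| of about 0.27 (133 per arm) or 0.31 (150 per arm), before credit for stratification. A reader might infer a firm upper limit of 2 points; that needs a weak correlation which the documents do not state. The disagreement rate of about 2 to 5% depends on the assumed r, center layout, block size and covariate effects. The conclusion of the trial is not endangered.

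**What to change.** **Preferred, before the Week 24 unblinding:**
- In SAP 7.1, make the primary analysis an ANCOVA of Week 24 change on treatment and continuous baseline HbA1c. The randomization HbA1c stratum may be added for consistency with the design. Any site term must use pooling fixed in advance.
- In Table 14.2-1.1, label that model's p-value, difference and 95% CI as primary. Keep the t-test as a sensitivity analysis and the fuller ANCOVA as supportive.
- Record the departure from the protocol-specified t-test in SAP section 10, which now reads as not applicable. SAP 7.2 defines the secondary t-tests by analogy with the primary one, so that wording needs aligning.

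**Minimum, if the t-test stays primary:** add its unadjusted mean difference and 95% CI and label the ANCOVA rows supportive in Tables 14.2-1.1, 14.2-1.2, 14.2-1.3 and 14.2-1.6, and in the FPG, weight and systolic and diastolic pressure tables that reuse those layouts. That is 4 HbA1c tables plus 4 for each of 4 other endpoints, 20 in all, but only three layouts to edit.

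Neither option needs more patients or new data. The minimum option leaves the protocol-specified test unchanged. The cost of delay is credibility: once Week 24 results are unblinded, choosing which estimate to headline would look data-driven.
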